11.1 TOXICITIES/SIDE EFFECTS

All toxicities will be graded using the NCI Common Toxicity Criteria for Adverse Events (CTCAE) version 4.0.

11.2 Anticipated adverse events

- Everolimus:

- Likely: stomatitis, xerostomia, nausea/vomiting, diarrhea, anemia, leucopenia, thrombocytopenia, increased transaminases, fatigue, dysglycemia, hyperlipidemia, hypophosphatemia, low bicarbonate, upper respiratory symptoms or infection, asthenia, peripheral edema, epistaxis, pruritus
- Less likely: rash, , dysgeusia, anorexia, weight loss, pneumonitis, dyspepsia, arthralgia, myalgia, hyperkalemia, hyponatremia, hypomagnesemia, hand-foot syndrome
- Rare but serious adverse events: chest pain, cardiac arrhythmias, cardiac arrest, pancreatitis, renal failure, a secondary malignancy, diabetes, bleeding and hepatitis B reactivation

- Letrozole:

- Likely: hot flashes, edema, hyperlipidemia, arthralgia, weakness, decreased bone mineral density, night sweats, headache, fatigue, dizziness, constipation, weight loss or gain, back pain, dyspnea, chest pain, nausea, vomiting, vaginal bleeding, renal failure, infection
- Less likely: cough, hypertension, diarrhea, anorexia, breast tenderness/soreness
- Rare but serious adverse events: cerebrovascular accident, venous thrombosis, myocardial infarction, and secondary malignancies

- Leuprolide:

- Likely: hot flashes, headache, depressed mood, pain or bruising at injection site, hyperhidrosis, insomnia, decreased bone mineral density, edema, hyperlipidemia, weight gain or loss, decreased libido, hypogonadism, acne, breast tenderness/soreness, breast enlargement, dysglycemia, hyperuricemia, infection at injection site, paresthesias, erectile dysfunction, pelvic or urinary tract discomfort
- Less likely: nausea, vomiting, dizziness, fatigue, arthralgia, myalgia, epistaxis, osteoporosis
- Rare but serious adverse events: chest pain, arrhythmia, thrombosis, fever, seizure, renal failure, hypersensitivity reaction, hemoptysis, hepatic failure

11.3 Reproductive risks

- Patients must not become pregnant or father a child while receiving protocol therapy due to potential risks to the unborn baby. Intrauterine device, double-barrier method, male partner sterilization or abstinence must be used during the duration of protocol therapy and until three months after the last dose of study therapy.
- Prescription oral contraceptives, contraceptive injections, and contraceptive patch are not approved methods of contraception in this study.
- Prepubescent patients have been shown to regain normal reproductive function after therapy with a GnRH agonist [67]. The long-term effects of aromatase inhibitors on reproductive function in prepubescent patients is unknown.
- Any pregnancy that occurs during study participation should be reported. To ensure patient safety each pregnancy must also be reported by the MSKCC Principal Investigator to Novartis within 24 hours of learning of its occurrence and/or receiving from the participating sites. The pregnancy should be followed up to determine outcome, including spontaneous or voluntary termination, details of the birth, and the presence or absence of any birth defects, congenital abnormalities, or maternal and/or newborn complications.

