- Concurrent antiviral therapy for hepatitis B is permitted.

- Women of childbearing potential must be practicing an effective method of birth control that may include intrauterine devices (both hormonal and non-hormonal are acceptable), double-barrier method, male partner sterilization or abstinence, before enrollment, and throughout the study and for 6 months after receiving the last dose of study drug. Men must agree to use a double barrier method of birth control and to not donate sperm during the study and for 6 months after receiving the last dose of study drugs. Sperm banking is acceptable for interested male patients enrolled on study prior to initiating treatment. Prescription oral contraceptives, contraceptive injections, and contraceptive patch are not approved methods of contraception and are not allowed in this study.
- Negative pregnancy test (serum hCG) result (applicable to women of child bearing potential) within 7 days before Cycle 1 Day 1 of study treatment.

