- Patients will undergo clinical and laboratory evaluations on weeks 1, 2 and 3 of Cycle 1. For all subsequent cycles starting with Cycle 2, evaluations will take place on weeks 1 and 3.
- Only clinical and laboratory assessments performed at Memorial Sloan Kettering Cancer Center or participating sites will be used to determine if patient will proceed with protocol treatment using the parameters listed below. Protocol assessments performed at a local oncologist may be used to determine treatment decisions at discretion of treating investigator and local oncologist.
- Before treatment on week 1 and 3 of each cycle: CBC and differential, comprehensive metabolic panel (Na, K, Cl, HCO₃, BUN, creatinine, AST, ALT, alkaline phosphatase, glucose), LDH, calcium, phosphorus, albumin, bilirubin, PT/INR, and ammonia. Treatment will only proceed if:
 - Hematologic: ANC $\geq 1.0 \times 10^9/L$, platelets $\geq 50 \times 10^9/L$
 - Renal: creatinine $\leq 2 \times$ upper limit of normal or creatinine Clearance of $\geq 60 \text{ cc/mL}/1.73 \text{ m}^2$ for patients > 16 years old. For patients ≤ 16 years of age, creatinine Clearance of $\geq 70 \text{ cc/mL}/1.73 \text{ m}^2$ or serum creatinine based on the following chart:

Creatinine clearance or radioisotope GFR $\geq 70 \text{ ml/min}/1.73 \text{ m}^2$ or serum creatinine based on age/gender as follows:

Age	Maximum Serum Creatinine (mg/dL)	
	Male	Female
10 to < 13 years	1.2	1.2
13 to < 16 years	1.5	1.4
≥ 16 years	1.7	1.4

The threshold creatinine values in this Table were derived from the Schwartz formula for estimating GFR (Schwartz et al. J. Peds, 106:522, 1985) utilizing child length and stature data published by the CDC.

- Hepatic: total bilirubin $\leq 2 \text{ mg/dL}$, alanine and aminotransferase levels $\leq 5 \times$ upper limit of normal for age.
- If hematologic, renal and hepatic function criteria are not met, treatment will be held and the patient will be reassessed weekly. Please refer to section 11.0 Toxicities/Side Effects for the

management of other adverse events during therapy.

- Fasting blood glucose and fasting lipid profile (total cholesterol, triglycerides, LDL, HDL) will be drawn on week 1 of each cycle beginning with cycle 2.
- Past FLL-HCC patients have also been referred for psychiatric services with depressive symptoms, immaturity and suicidal ideation as the most commonly observed symptoms. Participants on study will be psychiatrically evaluated as clinically indicated.

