17.2 Serious Adverse Event (SAE) Reporting

Any SAE must be reported to the IRB/PB as soon as possible but no later than 5 calendar days. The IRB/PB requires a Clinical Research Database (CRDB) SAE report be submitted electronically to the SAE Office at [contact]. The report should contain the following information:

Fields populated from CRDB:

- Subject's name (generate the report with only initials if it will be sent outside of MSKCC)
- Medical record number
- Disease/histology (if applicable)
- Protocol number and title

Data needing to be entered:

- The date the adverse event occurred
- The adverse event
- Relationship of the adverse event to the treatment (drug, device, or intervention)
- If the AE was expected
- The severity of the AE
- The intervention
- Detailed text that includes the following
 - A explanation of how the AE was handled
 - A description of the subject's condition
 - Indication if the subject remains on the study
 - If an amendment will need to be made to the protocol and/or consent form.

The PI's signature and the date it was signed are required on the completed report.

Pregnancy Reporting

Any pregnancy or fathering that may occur while on study or within 4 weeks after completion of therapy, must be reported as detailed in sections 11.2 and 17.3.

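### Section 11.3 ends contraception three months after the last dose, while the inclusion criteria require 6 months for women of childbearing potential and for men

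*Combined protocol and SAP*

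**What the plan says.** Section 6.2 (Subject Inclusion Criteria) makes contraception a condition of entry. Women of childbearing potential must use an effective method before enrolment, "throughout the study and for 6 months after receiving the last dose of study drug". Men must agree to use a double-barrier method and "to not donate sperm during the study and for 6 months after receiving the last dose of study drugs".

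Section 11.3 (Reproductive risks, numbered 11.2 in the table of contents) returns to the subject. It addresses both becoming pregnant and fathering a child, gives risk to the unborn child as the reason, lists acceptable methods, and requires them during protocol therapy and "until three months after the last dose of study therapy".

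**The concern.** The same safety rule is written twice with two durations. The length of the period after treatment matters only once a patient stops study drug, which may be long after the eligibility checklist was completed. At that point a site that consults Section 11.3 finds the shorter period. A patient who stops contraception in month 4 would then comply with Section 11.3 and breach the commitment made at entry.

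What is at stake is possible fetal exposure, together with an unclear standard for judging compliance across the four participating centers. Patients are eligible from age 12, and Section 1.0 describes a disease of adolescents and young adults, so reproductive age is likely to be common in this population.

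**Working it through.** No statistical calculation applies. The check is a direct comparison of the two texts, followed by a search for anything that would explain the difference.

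**Side by side**

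| Feature | Section 6.2, women | Section 6.2, men | Section 11.3 |
|---|---|---|---|
| Who is covered | Women of childbearing potential | Men | Patients who could become pregnant or father a child |
| Period starts from | Last dose of study drug | Last dose of study drugs | Last dose of study therapy |
| Period after last dose | 6 months | 6 months | Three months |
| Limited to an arm or a drug? | No | No | No |

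**Could the two be reconciled?**

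1. *Different starting point.* No. All three statements count from the last dose.
2. *Different patients.* No. Section 11.3 covers both sexes, and so do the two statements in Section 6.2.
3. *Different drugs or arms.* No. Neither section ties its duration to everolimus, letrozole or leuprolide, or to Arm A, B or C.
4. *Different methods.* No. The lists largely overlap: intrauterine devices, double-barrier methods, sterilization of a male partner, and abstinence. Both sections also exclude oral, injected and patch contraceptives. Section 6.2 holds men to a double-barrier method, but neither section makes the duration depend on the method.
5. *Superseded text.* No. Neither statement is in an amendment log or a summary of changes.
6. *A rule of precedence.* None was found.

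**Size of the gap**

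- Difference: 6 − 3 = 3 months.
- In weeks: one month = 365.25 / 12 / 7 = 4.348 weeks, so 3 × 4.348 = 13.04, or about 13 weeks.
- Share of the entry requirement covered by Section 11.3: 3 / 6 = 50%.
- Patients concerned: men and women of childbearing potential in all three arms, out of a maximum of 84. The document does not give their number.

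**The case against.** The strongest reply is that the practical risk is small. The two rules do not force a choice, because anyone who follows 6 months also satisfies three. The longer period is a condition of entry, and eligibility is confirmed by checklist and reviewed centrally with source documents (Sections 15.1 and 15.1.1). Harm would require a site to set that commitment aside and counsel from the toxicity section instead. All of this stands. It limits the importance of the point but does not remove the contradiction.

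A second reply is that, for men, the 6 months could be read as attaching only to sperm donation. The natural reading applies it to the whole agreement, contraception included. Even on the narrow reading, the conflict for women of childbearing potential is unchanged.

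A third reply is that the document does not show which duration was meant. That is correct, and the fix should allow for it.

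Three stronger readings are tempting but unsupported:

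- *Sites are directed to Section 11 for the contraception period.* Section 10.0 does say "Please refer to section 11.0 Toxicities/Side Effects for the" management of other adverse events, but this concerns adverse events during therapy. Section 17.2 says pregnancies "must be reported as detailed in sections 11.2 and 17.3", but this concerns reporting. Neither reference sends a site to Section 11.3 to find out how long contraception lasts.
- *The pregnancy-reporting window is also wrong because it is shorter than either contraception period.* Section 17.2 covers "Any pregnancy or fathering that may occur while on study or within 4 weeks after completion of therapy", and Section 17.2.1 gives sites the same 4-week limit for pregnancies. Nothing requires a reporting window to equal a contraception period. The instruction in Section 11.3 that "each pregnancy must also be reported by the MSKCC Principal Investigator to Novartis within 24 hours of learning of its occurrence" directly follows "Any pregnancy that occurs during study participation should be reported". It reads as a further duty for those same pregnancies, not an open-ended one. Extending the window would be a preference, not a correction.
- *The 3-monthly follow-up would pick up late pregnancies anyway.* Section 10.0 says only that patients may be contacted to monitor survival, and allows records or mortality lists to be checked instead. It is not set up to detect pregnancy.

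**Conclusion.** The inconsistency is real. Section 11.3 states a contraception period 3 months shorter than the one in Section 6.2, for the same starting point and overlapping patients, with nothing to reconcile them. It should be corrected because it is a conflicting fetal-safety instruction and the correction is nearly free. Its priority is modest: exposure arises only where a site counsels from Section 11.3, and there is no effect on the endpoint, sample size or analysis.

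The conclusion rests on the natural reading of the men's criterion and on the absence of any reconciling text in the protocol. A reader might infer that patients have been told three months. The documents do not show this, because the consent form was not available for review.

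**What to change.** In Section 11.3, replace three months with 6 months after the last dose. This is the stricter period and already binds patients at entry. The sponsor should confirm that 6 months is the intended duration, so that Sections 6.2 and 11.3 state one agreed period, and should check that the consent form gives the same figure.

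The cost is one phrase in the protocol and a check of the consent form. No visits, contacts or procedures are added, and nothing in the statistical design changes.

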11.4 Effects on bone health

Decreased bone mineral density with the increased risk of fractures and osteoporosis is a well known side effect of hormonal deprivation therapy in men and women. The 2003 ASCO guidelines on the use of bisphosphonates in women with breast cancer state that all postmenopausal women receiving aromatase inhibitors and premenopausal women with treatment induced menopause are considered at high risk of developing osteoporosis and should undergo a bone mineral density test [73]. Regardless of the result, healthy lifestyle modification should be encouraged and all patients should receive calcium and vitamin D supplementation. Oral bisphosphonates will be prescribed to women with osteoporosis as defined by a T score of ≤ -2.5 . Prophylactic IV bisphosphonates are not indicated to maintain bone health in women without bone metastases [73]. Similar recommendations apply to men based on guidelines of the National Osteoporosis Foundation (www.nof.org) and fracture risk as determined by the World Health Organization Fracture Risk Assessment Tool (FRAX) calculator available at <http://www.sheffield.ac.uk/FRAX/index.jsp>.

Bone mineral density in children and adolescents is not known to be affected by the use of aromatase inhibitors or GnRH agonists. Vertebral abnormalities have been reported in a specific population of boys with idiopathic short stature who were treated with letrozole [68] but not other pediatric patient populations treated with aromatase inhibitors. Consensus guidelines recommend that children and adolescents receive daily calcium and vitamin D supplementation as well as engage in skeletal-loading exercise while receiving a GnRH agonist [67]. The guidelines also state that bone age should be followed periodically during therapy [67].

12.1 CRITERIA FOR THERAPEUTIC RESPONSE/OUTCOME ASSESSMENT

Tumor responses will be evaluated using the revised RECIST version 1.1 guidelines [148].

12.2 Measurement of tumors

All lesions should be measured and recorded using metric notation. The same assessment method and technique should be used to characterize each identified and reported lesion at baseline and on follow-up.

12.2.1 Measurable disease

- Tumor lesions must be accurately measurable in at least one dimension (longest diameter in plane of measurement recorded) and have a longest diameter of ≥ 10 mm by CT (slice thickness ≤ 5 mm) or MRI.
- Pathologically enlarged, measurable lymph nodes are ≥ 15 mm in the short axis on CT (slice thickness ≤ 5 mm) or MRI. Only the short axis is to be measured at baseline and on follow-up scans.
- Lytic or mixed lytic-blastic bone lesions with a soft tissue component are considered measurable disease if the soft tissue component is measurable by CT or MRI and meets the size criteria for measurability.
 - Bone scan, PET and plain films are inadequate techniques to measure bone disease, but can be used to verify the presence or disappearance of bony lesions.
- Lesions representing cystic metastases are considered measurable if they meet the size criteria for measurability. Where possible, non-cystic lesions are preferred as target lesions.
- Lesions sitting in an area previously irradiated or treated with locoregional therapy are only considered measurable if there has been evidence of progression in those lesions.

12.2.2 Non-measurable disease

- Includes all lesions < 10 mm in longest diameter or pathological lymph nodes ≥ 10 or < 15 mm on short axis and truly non-measurable lesions (leptomeningeal metastases, ascites, pleural/pericardial effusions, lymphangitic skin or lung involvement, abdominal masses/organomegaly found on physical exam that is not reproducibly measurable by imaging studies, osteoblastic metastases).

12.2.3 Reporting of target lesions

- The sum of the longest diameter of all measurable non-lymph node target lesions and the short axis of all measurable target lymph nodes equals the baseline sum diameters. This value will be used for future comparisons with subsequent imaging to evaluate objective tumor responses.

12.2.4 Reporting of non-target lesions

- All non-target lesions, disease sites, and pathological lymph nodes do not require measurement, but should be recorded at baseline. Non-target lesions can be described as “present”, “absent”, or showing “unequivocal progression.” Multiple non-target lesions in the same organ can be reported as a single item.

12.2 Response criteria

12.2.1 Evaluation of target lesions

- Complete response (CR): disappearance of all target lesions and regression of all pathological lymph nodes (target and non-target) to < 10 mm in short axis diameter.
- Partial response (PR): $\geq 30\%$ reduction from baseline in the sum of diameters all target lesions.
- Progressive disease (PD): $\geq 20\%$ increase in the sum of diameters of all target lesions from the smallest sum on study AND an absolute increase of at least 5 mm. Also includes the appearance of any new lesion(s).
- Stable disease (SD): Meeting neither criteria for PR or PD using the smallest sum on study as the reference.

12.2.2 Evaluation of non-target lesions

- Complete response (CR): disappearance of all non-target lesions. All lymph nodes must be < 10 mm in short axis diameter (i.e. non-pathological).
- Progressive disease (PD): unequivocal progression of existing non-target lesions or the appearance of new lesion(s).
- Non CR/non PD: Persistence of ≥ 1 non-target lesion(s).

12.2.3 Evaluation of patients with both measurable (target) and non-measurable (non-target) disease

- In order to have PD based on non-target lesions, there must have been sufficient growth of the non-target lesions such that, even in the presence of SD or PR of target lesions, the overall tumor burden has increased enough to warrant discontinuation of therapy.
- A modest increase in the size of ≥ 1 non-target lesions, in the presence of SD or PR of target lesions, is insufficient to define unequivocal disease progression.

12.2.4 Best overall response

- This is the best response documented from the start of treatment to disease progression or recurrence according to the table below.

Target lesions	Non-target lesions	New lesions	Overall response
CR	CR	none	CR
CR	Non CR/non PD	none	PR
CR	Not evaluated	none	
PR	Non PD or not all evaluated	none	SD
SD	Non PD or not all evaluated	none	
Not all evaluated	Non PD	none	Not evaluable
PD	Any	Yes/no	PD
Any	PD	Yes/no	
Any	Any	Yes	

CR = complete response; PR = partial response; SD = stable disease; PD = progressive disease

- Patients with a global deterioration of health status warranting discontinuation of therapy without objective disease progression at that time will be reported as “symptomatic deterioration.” Every effort should be made to document disease progression even after discontinuation of therapy.

13.0 CRITERIA FOR REMOVAL FROM STUDY

Study therapy will continue until/unless there is:

[figure not shown]
- Disease progression as defined by RECIST 1.1 criteria
- Clinical progression
- Unacceptable toxicity
- Patient withdrawal of consent
- Patient noncompliance
- Intercurrent illness that prevents further administration of treatment. Inability to take EDT and everolimus simultaneously for patients who receive combination therapy. In very special circumstances, study chair may allow continuation of everolimus or EDT pending the approval of the local IRB.
- General or specific changes in the patient’s condition rendering him/her unacceptable for further treatment in the judgment of the investigator. Delay of therapy for > 4 weeks. If more than 4 weeks are required for recovery, the study chair may allow continuation of everolimus or EDT pending the approval of the local IRB.
- Patients who are removed from the study for any of the above reasons will continue to be monitored for survival every 3 months unless consent for continued follow-up is withdrawn.

14.0 BIOSTATISTICS

Primary efficacy endpoints for Part 1 of protocol

- The primary efficacy endpoints for Part 1 of the study is progression-free survival at 6 months (PFS6).
- A progression event refers to the first evidence of radiographic disease progression, clinical progression as determined by study investigators, or death.
- Imaging performed in 6 months will be used to determine PFS6.
- PFS6 will be defined as the percentage of patients who are alive and have not experienced a progression event as defined above at 6 months from the date that study therapy was initiated. Patients that come off study before the 6 months scan will be considered events for the primary endpoint analysis.
- PFS6 will be assessed using a Simon's minimax two stage design, hypothesizing an improvement in PFS6 from 40% to 64% with the study regimen. Sixteen patients will be enrolled onto each of Arms A, B and C for a total of 48 patients in the first stage. Accrual will stop till the progression status at 6 months is obtained on all 16 patients in each arm. If 6 or less patients in one arm are progression free at 6 months the regimen in that arm will be terminated; otherwise, if 7 or more patients are alive and progression free at 6 months, enrollment will be extended in that arm to 28 patients (maximum total of 84 patients). At the end of stage 2, the respective regimens will be declared promising if 15 or more of the 28 patients in each arm are alive and progression free at 6 months. The design assumes a type I error (falsely accepting a non-promising therapy) and type II error (falsely rejecting a promising therapy) both set to 10%.

Figure 4: Simon's minimax 2 stage design (schematic applicable for each study arm)

- The probability of early termination due to drug inefficacy is 53%. In the event that 2 or more arms show promising activity, we will use the “pick the winner” format based on the randomized phase II clinical trials approach proposed by Simon et al. In this case, the regimen that has at least 15 patients progression free at 6 months and exceeds by at least 2 patients the number of progression free patients in the second best arm would be declared the winner. The probability of selecting the better regimen is 85%; the probability that no regimen is selected is 7%, while the probability of a tie is approximately 6% [149].

Secondary endpoints

- Secondary endpoints are:
 - Median PFS
 - Median overall survival (OS)
 - Objective response rate by RECIST 1.1 guidelines
 - Rate of conversion to resectable status
 - Safety and toxicity
 - Correlative serum and tissue biomarker studies.
- Kaplan-Meier PFS will be measured from the date that study therapy is initiated until the date of

first evidence of radiographic disease progression, global clinical deterioration as determined by study investigators, or death.

- Kaplan-Meier OS will be measured from the date that study therapy was commenced until the date of death.
- Objective responses will be reported using RECIST guidelines (version 1.1). Objective response will be estimated using binomial proportions and exact 95% CIs will be provided.
- Conversion to resectable status to be determined by hepatobiliary surgeons in conjunction with radiological assessment of response to therapy.
- Adverse events/toxicity will be monitored and recorded using the CTCAE version 4.0 and summarized descriptively.
- Baseline serum measurements will be correlated with PFS6 (binary endpoint) using Fisher's exact test for categorical serum measurements and using Wilcoxon rank sum test for continuous measurements. For each time point at which serum measurements are collected, changes in the different binary serum markers from baseline will be correlated with PFS6 using conditional logistic regression to account for the paired nature of the data while Wilcoxon signed-rank test will be used for continuous measurements.
- Associations between baseline tissue biomarkers and PFS6 will be assessed using Fisher's exact test for categorical biomarkers, trend tests for ordinal biomarkers and Wilcoxon rank-sum test for continuous biomarkers. For patients undergoing surgery, changes in tissue biomarkers from baseline to surgery will be summarized descriptively in an exploratory fashion.

Exploratory analysis for Part 2 of protocol (combination therapy).

- PFS will be evaluated for patients who were on Arm A (everolimus) or Arm B (EDT) during Part 1 of the study who subsequently received combined everolimus + EDT during Part 2.
- PFS will be measured as the time from the start of the combination therapy till progression or death whichever comes first.

Biomarker analysis and data interpretation

- Baseline tissue biomarkers will be correlated with PFS6.
- Baseline levels of hormones will be correlated with PFS6.
- Baseline levels of tumor markers will be correlated with PFS6.
- Following initiation of EDT, castration will be considered effective if serum estrogens are in the postmenopausal range, serum testosterone is in the castration range and FSH below the detection threshold as per the cutoffs established at the respective study site laboratories. The achievement of chemical castration will be correlated with PFS6.

- The maximum change in levels of tumor biomarkers from baseline will be correlated with PFS6.

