15.2 Randomization

In Part 1 of the study, patients will be randomized to Arm A (everolimus), Arm B (EDT) or Arm C (everolimus + EDT). Randomization will be performed centrally. Study investigators and participants will not be blinded to therapy assignment. Patients will be stratified by study site.

Patients will be registered and randomized using the Clinical Research Database (CRDB) and assigned an MSKCC CRDB number. This number is unique to the patient and must be written on all data and correspondence for the patient. This protocol patient number and the treatment arm assignment will be relayed back to the study staff at the registering site via email and will serve as enrollment and treatment arm confirmation.

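### PFS and OS are dated from first dose in an open-label randomized trial with no named analysis set, so never-treated patients drop out of the Kaplan-Meier estimates and their PFS6 status is left to inference

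*Combined protocol and SAP*

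**What the plan says.** Section 14.0 (Biostatistics) starts all three time-based endpoints at the beginning of treatment:

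- PFS6 is assessed "at 6 months from the date that study therapy was initiated".
- For PFS, "Kaplan-Meier PFS will be measured from the date that study therapy is initiated until the date of" progression, clinical deterioration or death.
- For OS, "Kaplan-Meier OS will be measured from the date that study therapy was commenced until the date of death".

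For the primary endpoint only, Section 14.0 adds: "Patients that come off study before the 6 months scan will be considered events for the primary endpoint analysis".

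Section 15.2 (Randomization) places assignment before treatment: "Patients will be registered and randomized using the Clinical Research Database (CRDB) and assigned an MSKCC CRDB number". The arm is then emailed to the site, and "Study investigators and participants will not be blinded to therapy assignment". Section 6.2 foresees some interval before the first dose: "Sperm banking is acceptable for interested male patients enrolled on study prior to initiating treatment".

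The documents do not name an analysis population, limit the time from randomization to first dose, or say whether a patient who never starts is counted or replaced. Section 13.0 provides survival follow-up every 3 months, but for patients removed for reasons listed as grounds for ending study therapy.

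**The concern.** A patient who learns the assigned arm and then declines or deteriorates before the first dose has no start date. For Kaplan-Meier PFS and OS that patient cannot be entered, and Section 13.0 does not clearly require survival follow-up. The published curves would describe patients who started, not patients who were randomized.

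For PFS6 the issue is narrower. The off-study rule would normally make such a patient a failure, but it follows a definition that presupposes a first dose, and nothing prevents a site or analyst from replacing the patient to reach 16 or 28 treated. Arms B and C involve chemical castration in a population that includes adolescents and young adults, and Arm A in Part 1 does not, so non-starting could differ by arm. The between-arm step names a winner on a lead of 2 patients. One or two patients handled differently in one arm could change that result.

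**Working it through.** **Inputs from Section 14.0.** The design is "hypothesizing an improvement in PFS6 from 40% to 64% with the study regimen", so p0 = 0.40 and p1 = 0.64. Stage 1 has 16 patients per arm, and the arm stops at 6 or fewer successes. The total is 28 per arm, promising at 15 or more. Type I and type II error are set at 10% each, early termination is stated as 53%, and the winner needs a lead of at least 2.

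**Inputs not in the documents (assumptions).** f is the share of randomized patients who never start, taken as 3%, 5%, 7% and 10% (28 × 0.03 = 0.8 to 28 × 0.10 = 2.8 patients per arm). s is the PFS6 rate those patients would have had, taken as 0%, 20% and 40%.

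**Step 1. Reproduce the design.** For true rate p,

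P(promising | p) = Σ over x = 7 to 16 of b(x; 16, p) × P(Y ≥ 15 − x), with Y ~ Binomial(12, p).

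- p = 0.40: 0.0989, so type I error is 9.9%.
- p = 0.64: 0.9019, so power is 90.2%.
- Early termination: P(X ≤ 6 | 16, 0.40) = 0.527, against the stated 53%.

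The plan's figures are right.

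**Step 2. Non-starters excluded and replaced.** If the rate among all randomized patients is truly 40%, the rate among starters is (0.40 − f × s)/(1 − f). For example, f = 0.10 and s = 0 gives 0.40/0.90 = 0.444; f = 0.10 and s = 0.20 gives 0.38/0.90 = 0.422. Putting these into the Step 1 formula gives the chance of declaring the arm promising:

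| f | s = 0 | s = 20% | s = 40% |
|---|---|---|---|
| 3% | 12.5% | 11.1% | 9.9% |
| 5% | 14.5% | 12.1% | 9.9% |
| 7% | 16.8% | 13.1% | 9.9% |
| 10% | 21.0% | 14.8% | 9.9% |

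The s = 0 column is the upper bound.

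**Step 3. Non-starters kept as failures, with 64% holding only among starters.** The rate among all randomized patients is 0.64 × (1 − f).

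- f = 5%: 0.64 × 0.95 = 0.608, power 82.6%.
- f = 10%: 0.64 × 0.90 = 0.576, power 72.4%.

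**Step 4. The winner rule, by simulation (400,000 trials).** The documents do not state the rates behind their selection figures. Assuming 40%, 40% and 64%, the simulation gives 84.4% for the better regimen, 7.9% for none and 5.3% for no clear winner, against the stated 85%, 7% and about 6%. Now assume all three arms have 50% among all randomized, and one arm alone replaces its non-starters, all of whom would have failed. That arm's rate becomes 0.50/(1 − f). Its chance of being named winner is 26% at f = 5% and 35% at f = 10%, against 20% with no loss.

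**The case against.** The strongest reply concerns the primary endpoint. Section 15.2 treats registration, randomization and enrollment as one act, and Section 14.0 counts patients enrolled to each arm and waits for the 6-month status of all 16. Together with the off-study rule, this makes a patient who is randomized, declines and leaves one of the 16 and a failure. A binary outcome scored that way needs no time origin. A reader might infer from the first-dose wording that never-treated patients have no PFS6 and fall out of the primary analysis. The documents do not support that: no text excludes or replaces them, and the plain reading counts most of them as failures. What stands of the concern is that the rule neither names them nor bars replacement.

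A reader might also infer that the randomized comparison as a whole is broken. That goes too far as well. Each arm is judged first against a fixed 40%, the winner rule applies only if two or more arms are promising, and no between-arm test of PFS or OS is planned. The Kaplan-Meier gap affects descriptive estimates.

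Third, differential loss is conjecture. Consent covers the design and risks beforehand, two of the three arms contain EDT, and Arm A patients may receive it in Part 2. Sperm banking shows possible delay, not loss, and declining for fertility reasons is not a sign of poor prognosis. This is a fair reason to treat the s = 0 figures as an extreme.

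None of this answers the Kaplan-Meier point, for which the plan has no rule.

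**Conclusion.** The concern holds in this limited form. For Kaplan-Meier PFS and OS the gap is definite: the stated origin leaves out every randomized patient who never starts. For PFS6 it is an ambiguity that the off-study rule probably resolves the right way, but the plan should say so because its decisions rest on counts of 16 and 28 and a lead of 2.

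The size is unknown, since the documents give no non-starting rate. If non-starters were replaced, per-arm type I error would lie between 9.9% (they would have done as well as the 40% average) and 21.0% (10% loss, all failures). Under the plain reading, with non-starters already counted as failures, this inflation does not arise. The winner-rule figures also rest on an assumed common rate of 50% and on one arm alone replacing its non-starters. The design's stated error rates and early-termination figure are not in question.

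**What to change.** In Section 14.0:

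1. Define the primary analysis set as all randomized patients, by assigned arm.
2. State that patients who never start study therapy are PFS6 events and are not replaced toward the 16 or 28.
3. Date Kaplan-Meier PFS and OS from randomization.
4. Keep the from-first-dose analyses as supportive.

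In Section 13.0, extend the survival follow-up to randomized patients who were never treated, subject to consent.

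PFS6 need not be re-dated for patients who start: the 6-month scan, which Section 10.0 times with a window of two weeks either side, can stay. Sample size and cut-offs also stay.

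The cost is a text amendment, follow-up of a probably small number of patients, and possibly power. If the sponsor had planned to replace non-starters and expects 64% only among starters, Step 3 gives the loss: from 90% to 83% at 5% non-starting and 72% at 10%. If non-starters were always meant to count as failures, the wording adds no power cost. Either way the rule should be fixed before outcome data by arm are examined.
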